1.14 Will participants be randomized?

Yes

- **1.15** Will any of the following be used to collect information from the participant or others?
 - Screening questions or screening/eligibility questionnaires
 - Surveys
 - Questionnaires
 - Stimuli
 - Any other written assessments

Yes

Attachment Name	Category	Version	Date Attached
KSADS DSM 5 SCREEN edited.pdf	Subject Data Collection Instruments	1	06/24/19
Formative Questionnaire.docx	Subject Data Collection Instruments	1	11/06/19
Patient Health Questionnaire.pdf	Subject Data Collection Instruments	2	12/27/18
Testimonial Questionnaire.docx	Subject Data Collection Instruments	1	11/06/19
Eating Disorders Examination Questionnaire (EDE-Q) Parent.docx	Subject Data Collection Instruments	2	08/14/18
Consideration of Future Consequences Scale- Parent.docx	Subject Data Collection Instruments	2	08/14/18
Parent Clinical Interview 12.5.docx	Subject Data Collection Instruments	6	12/12/19
Receipt Collection Instructions.pdf	Subject Data Collection Instruments	1	01/22/20
Grocery Shopping Task.docx	Subject Data Collection Instruments	1	01/22/20

Delay Discounting Task- Parent&Child.docx	Subject Data Collection Instruments	2	08/14/18
Kids Eating Disorders Survey- Child.docx	Subject Data Collection Instruments	2	08/14/18
Child Clinical Interview 12.5.docx	Subject Data Collection Instruments	4	12/12/19
Home Food Inventory.docx	Subject Data Collection Instruments	1	03/12/20
PHQ Probes.docx	Subject Data Collection Instruments	1	12/11/19
Sociodemographic Questionnaire- Parent.docx	Subject Data Collection Instruments	1	11/09/18
Consideration of Future Consequences Scale- Child.docx	Subject Data Collection Instruments	2	08/14/18
Shelf Life Survey.xlsx	Subject Data Collection Instruments	1	06/15/20
KSADS DSM 5 Supp1 DepressiveDO edited.pdf	Subject Data Collection Instruments	1	06/21/19
TT Frequency of Use Question.docx	Subject Data Collection Instruments	1	10/02/19

- **1.16** Does this project involve creating any audio, video, or photographs? Yes
- **1.17** Does the study include any form of deception (e.g., providing participants with false information, misleading information, or withholding information about certain study procedures)? Examples:
 - Procedure includes a cover story that provides a plausible but inaccurate account of the purposes of the research.
 - Participants will be provided with false information regarding the particular behaviors of interest in the research.
 - Procedures include a confederate pretending to be another participant in the study.
 - Participants will be told that the research includes completion of a particular task, when in fact, that task will not be administered.
 - Study is designed to introduce a new procedure (or task) that participants are not initially told about.

No

- **1.18** Indicate any payments or reimbursements to participants (check all that apply)
 - CashGift or Debit Card
- 1.19 Does this study have a plan to have an individual or committee review combined data from all participants on a periodic basis (such as summary or aggregate safety and/or efficacy data)? No
- **1.20** What have you done to minimize any risks?
 - No foreseeable risks
 - Psychological consultation and/or referrals readily available
 - **1.21** What are the potential benefits related to this project for:
 - the participant (if any)
 - benefits to society (if any)

There are many potential benefits of the proposed research. Participants in the study could gain new knowledge on how episodic future thinking influences inter-temporal decision making. All participants in all groups are taught methods for healthier grocery shopping, eating and living; therefore, depending on the behavior changes of the participants, it could result in a healthier eating behaviors and a healthier home environment. This in turn could result in potential weight loss for the entire family in the home. If participants do lose weight in the study, it could decrease their risk of weight-related disease such as type 2 diabetes and heart disease.

1.22 Provide a summary of the analysis methods you will use, including, if applicable, the data points or outcomes you will analyze.

Cohort 1:

Preliminary analyses:

Preliminary analyses will be conducted to ensure groups are similar based on demographic characteristics (age, BMI, race/ethnicity, SES).

Primary analyses:

Between group ANOVAs will be performed to make sure the two groups have similar continuous characteristics (age, BMI for adults/percent over BMI for children) and chi-square analyses will be performed to ensure the groups have similar categorical characteristics (race/ethnicity, SES). If a group difference is found, the variable will be entered as a covariate in subsequent analyses.

Two-way repeated measures ANOVAs will then be conducted to determine differences in BMI/percent over BMI, weight, and waist circumference, between the EFT and HT groups over time. Data points will be collected at weeks 2 (baseline), 7, 10, 14 (incentive program ends), 18, and 26 of the program. We hypothesize:

1- The EFT and HT group will both have a reduction in BMI/percent over BMI, weight, and waist circumference from baseline throughout the monetary incentives program (week 7, 10, 14).

2- The EFT group will have a greater reduction in BMI/percent over BMI, weight, and waist circumference from baseline throughout the monetary incentives program (week 7, 10, 14) than the HT group.

3- The EFT group will maintain the reduction in BMI/percent over BMI, weight, and waist circumference from baseline after the termination of the monetary incentives program (week 18, 26).

4- The HT group will not maintain the reduction in BMI/percent over BMI, weight, and waist circumference from baseline after the termination of the monetary incentives program (week 18, 26).

Secondary analyses:

A two-way repeated measures ANOVA will be conducted to determine differences in delay discounting between the EFT and HT groups over time. Data points will be collected at weeks 2 (baseline), 7, 10, 14 (incentive program ends), 18, and 26 of the program. We hypothesize:

- 1- The EFT group will have a reduction in delay discounting over time (7, 10, 14, 18, 26) compared to baseline.
- 2- The HT group will not have a reduction in delay discounting over time (7, 10, 14, 18, 26) compared to baseline.

3- The EFT vs. the HT group will have a reduction in delay discounting over time (7, 10, 14, 18, 26).

Regression analyses will also be conducted to determine whether baseline characteristics predict outcome variables (BMI for adults/percent over BMI for children, weight, waist circumference, and DD). These characteristics will be collected from baseline surveys including the Consideration of Future Consequences Scale, Living to 75 Assessment, and Palatable Eating Motives Scale. First, zero order correlations between each predictor and the outcome variables will be established, and then significant predictors will be entered in a multiple regression model that includes demographic characteristics and the significant predictors. This will provide the opportunity to assess what individual characteristics predict child and adult success. In addition, we will assess the influence of parental success on child success in a multiple regression model, again controlling for demographic characteristics.

Cohort 2:

Preliminary analyses will be conducted to ensure groups are similar based on demographic characteristics (age, BMI, race/ethnicity, SES).

Primary analyses: Between group ANOVAs will be performed to make sure the two groups have similar continuous characteristics (age, BMI for adults/percent over BMI for children) and chi-square analyses will be performed to ensure the groups have similar categorical characteristics (race/ethnicity, SES). If a group difference is found, the variable will be entered as a covariate in subsequent analyses.

Two-way repeated measures ANOVAs will then be conducted to determine differences in BMI/percent over BMI and weight between the EFT and HT groups over time. Data points will be collected at sessions 3 (baseline), 11 (monetary incentives end), 19, 20. We hypothesize:

1- The EFT and HT group will both have a reduction in BMI/percent over BMI and weight, and waist circumference from baseline throughout the monetary incentives program (session 11).

2- The EFT group will have a greater reduction in BMI/percent over BMI and weight throughout the monetary incentives program (session 11) than the HT group.

3- The EFT group will maintain the reduction in BMI/percent over BMI and weight from baseline after the termination of the monetary incentives program (session 19, 20).

4- The HT group will not maintain the reduction in BMI/percent over BMI and weight from baseline after the termination of the monetary incentives program (session 19, 20).

Secondary analyses: A two-way repeated measures ANOVA will be conducted to determine differences in delay discounting between the EFT and HT groups over time. Data points will be collected at sessions 2 (baseline), 11 (incentive program ends), 19, and 20. We hypothesize:

1- The EFT group will have a reduction in delay discounting over time (11, 19, 20) compared to baseline.

2- The HT group will not have a reduction in delay discounting over time (11, 19, 20) compared to baseline.

3- The EFT vs. the HT group will have a reduction in delay discounting over time (11, 19, 20).

Regression analyses will also be conducted to determine whether baseline characteristics predict outcome variables (BMI for adults/percent over BMI for children, weight, and DD). These characteristics will be collected from baseline surveys including the Consideration of Future Consequences Scale, Living to 75 Assessment, and Palatable Eating Motives Scale. First, zero order correlations between each predictor and the outcome variables will be established, and then significant predictors will be entered in a multiple regression model that includes demographic characteristics predict child and adult success. In addition, we will assess the influence of parental success on child success in a multiple regression model, again controlling for demographic characteristics.

The results of this study will be analyzed graphically as well as assessing the degree of change from baseline to treatment across the three replications.

1.23 Provide the rationale or power analysis to support the number of participants proposed to complete this study. This is the first study of this kind, therefore, we were unable to conduct a power analysis. Additionally, a power analysis is not applicable to this multiple baseline design. We are collecting weekly data from participants and will have enough data points to ensure we will be able to achieve the study objectives. The results of this study will be analyzed graphically as well as assessing the degree of change from baseline to treatment across the three replications. For an example of a study that utilized a multiple baseline design, see:

- 1.25 Will any data from this project be stored for use in future research studies? No
- 1.26 Does this project involve the collection or use of biological samples or genetic data? No
- 1.27 Are you requesting institutional certification to contribute human data or samples to a repository or database for broad sharing (public or restricted access)? No

2. Participants

- 2.1 Will there be any adult participants? Yes
 - **2.1.a** How many adult participants do you expect to consent or enroll under a waiver for this project? 85
 - **2.1.b** What is the age of the youngest adult participant? 18.0
 - **2.1.c** What is the age of the oldest adult participant? No age limit
- 2.2 Will there be any minor participants? Yes
 - **2.2.a** How many minor participants do you expect to consent or enroll under a waiver for this project? 85
 - **2.2.b** What is the age of the youngest minor participant? 10.0
 - **2.2.c** What is the age of the oldest minor participant? 14.0
- 2.3 Will there be any emancipated minor participants? No
- **2.4** You may indicate in the table below either a single, or multiple approaches for obtaining assent from minors in your study.
 - If you will use the same method for all minors, you only need to enter one row.
 - If you will use different assent methods depending on age, add multiple rows, breaking the minors into different age range(s)
 - Indicate in each row the appropriate assent method(s) for each age range. Be sure to include the entire age range of your minor population.

Youngest	Oldest	Obtain Assent?	Assent Method(s)	Rationale
10.0	14.0	Yes	 Sign an assent document 	Participants who are minors will be between ages 10 and 14 and therefore, unable to provide legal consent to participate in the study.

2.5 Will any minors reach the age of majority during their participation in this study?

No

- 2.6 Will any of the participants enrolled be in foster care or Wards of the state? No
- 2.7 Do you plan to recruit/enroll non-English speaking people? No
- 2.8 Do you propose to enroll any of the following in this study as participants?
 - Employee of the PI or employee of a research team member
 - Individual supervised by PI or supervised by member of research team
 - Individual subordinate to the PI or subordinate to any member of the research team
 - Student or trainee under the direction of the PI or under the direction of a member of the research team

No

- 2.9 Is this project about pregnant women?
- 2.10 Will this project involve fetuses?
 - No
- 2.11 Does this project involve the use of fetal tissue from any source?
 - No
- 2.12 Does this project recruit adult participants who may be incompetent or have limited decision-making capacity on initial enrollment into the study?
- 2.13 Does this project involve prisoners as participants? No

3. Performance Sites

- **3.1** Indicate type of site(s) where research will occur (check all that apply):Academic Institution
- **3.2** Where will project procedures take place (check all that apply)?School of Medicine
- **3.3** Is this project also being conducted by other researchers at their own sites (e.g. a multi-site collaborative project)? Yes
 - **3.3.a** What is your site's role(s) for this project (check all that apply)?
 - Clinical/participating site
 - Central laboratory or laboratory analysis
 - · Data analysis, statistical analysis or data management
 - **3.3.g** What are participating site roles for this project?
 - Data analysis, statistical analysis or data management [name] and [name]- University of Buffalo (UB)
 - Other [name] and [name] will monitor case management phone calls to ensure each researcher provides quality support for each family.

5. Privacy & Confidentiality

- **5.1** Indicate your plans to protect the privacy interests of the participants during the conduct of the study (check all that apply):
 - Only the minimum necessary private information is collected for the purposes of the study
 - Any procedures or interventions conducted as part of the study will be conducted in private setting to the extent possible
 - Recruitment/consent will occur in a private setting
 - Participants will be able to ask questions in a private setting
- **5.2** Are you collecting or using the Social Security Number of any participants for any purpose? Yes

5.2.a Provide the intended usage of SSN:

- To provide compensation to participants
- **5.3** Project uses paper or hard copy consents, surveys, data collection forms, research subject binders, or other hard copy materials (check all that apply):

Yes

- All materials are stored in secured environment
- · Access is limited to research team members only
- **5.4** Project collects, stores and/or transmits electronic data on mobile devices, desktop computers, servers including cloud servers, email, or any other information in electronic form (check all that apply):
 - Password protected
 - Access is limited to research team only
 - Data are encrypted
 - Data in Qualtrics for General Use
 - Other Data sent to the participants from the researchers and between researchers on the team will be sent via Washington University's secured network using a secured email address. Data sent between researchers on the team will also be password protected. However, we cannot be sure the participants are using equally secured means of communicating with the researchers. They are encouraged in the consent form to use secured means of sending personal information.
- 5.5 Project collects or uses biologic specimens (check all that apply): No
- **5.6** Identify any additional protections in place for data and or samples (check all that apply):
 - No additional protections

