1.7 Describe EACH of your participant populations

- Include description of any control group(s)
- Specify the Inclusion/Exclusion criteria for EACH group

Cohort 1:

Experimental Group- Episodic Future Thinking (EFT) Group; Control Group- CONTROL

Both groups will include parent/child dyads with overweight or obesity and inclusion/Exclusion criteria will be the same for both groups:

Inclusion:

- 1- Child age between 10-14
- 2- Child height and weight that calculates to a BMI above the 85th percentile (BMI in overweight/obesity range)
- 3- Parent height and weight that calculates to a BMI above 24.9 (BMI in overweight/obesity range)
- 4- Possession of at least one electronic device (per family) with WiFi capabilities (e.g. smartphone, tablet, computer) 5- Home internet access
- 5- Home Internet access

6- Motivation to lose weight

Exclusion:

1- Disordered eating patterns (e.g. binge-eating disorder, extreme weight-loss behaviors)

2- A family history of eating disorders (siblings, children, parents, or grandparents)

3- Medical conditions that are known to interfere with weight-loss (e.g. type 1 diabetes, thyroid disease)

4- Medical conditions that may affect their ability to use the computer for a prolonged period of time or follow study protocol

5- Psychopathology or disabilities that would limit adherence to protocol (e.g. depression, suicidality, ADHD). Participant will only be excluded if the disability would not allow them to adhere to protocol. Just having the disability does not exclude them. Suicidality would be automatically be exclusionary)

6- Substance use, abuse, or dependence (e.g. binge drinkers, illicit substance users, alcoholics)

7- Plans to start or stop a medication that may affect appetite/weight-loss during the intervention period

8- Have started a medication within 6 months that is affecting appetite/weight-loss

9- Plans to move out of the area during the treatment period

10- Pregnancy/breastfeeding or plans of becoming pregnant during the study period

11- Is participating in another weight-loss program

12- Can not successfully record eating behavior in the MyFitnessPal app

13- A) Had bariatric surgery less than one year ago

B) If the potential participant had bariatric surgery over a year ago, their weight has not been stable for at least 6 months

Cohort 2:

The same as Cohort 1 with an additional exclusionary criterion:

- Can not successfully record eating behavior in the MyFitnessPal app

Cohort 3:

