EFT or CONTROL Cue Retrieval: The experimenter will then train participants in both groups on how to retrieve cues from their cell phone or alternative WiFi device, to pay attention to and think about the cues, and how to adhere to the study's expectations for utilizing to the cues. Participants will be told to use their cues any time they need to, especially around eating episodes, using the prompt response website - Mobile Audio Management and Response Tracker (MAMRT) (Sze, Daniel, Kilanowski, Collins, Epstein, 2015).

At-home weighing: Participants will send their weights to the researchers once per week (when they aren't visiting the lab outlined in the "Intervention Sessions" section below) from a wireless scale provided to them by the researchers. During this baseline session, participants will be given a tutorial on how to use the wireless scale and associated application to send their weekly weights. Participants are also going to be asked to send a video of themselves weighing to ensure a valid weight result. The researchers will instruct participants on how to record and send these videos. The families will email their weight videos directly to the contact person of the study, [name] ([contact]). [name] will store the weight videos on the secured lab drive in a password protected folder. [name] is the only person who will have access to the weight videos.

FamZoo: Participants will be receiving their monetary incentives through the FamZoo platform. FamZoo is a prepaid debit card system that will allow the researchers to immediately transfer money to the separate parent or child debit card if the parent/child meet their weight loss goals. Participants will be instructed on how to use the FamZoo platform during the baseline session and will sign up for the account during session.

Intervention Sessions: There will be 24 weekly sessions following the screening and baseline sessions. Participants will only receive monetary incentives during the first 12 weeks. The incentive program is outlined below:

Incentives for individual weight loss (per person) Parent receives this amount if he/she loses 1 lb that week Child receives this amount if he/she loses 1/2 lb that week

Session 3 \$0.50 Session 4 \$1.00 Session 5 \$2.50 Session 6 \$5.00 Session 7 \$5.00 Session 8 \$5.00 Session 9 \$5.00 Session 10 \$5.00 Session 11 \$5.00 Session 12 \$5.00 Session 13 \$5.00 Session 14 \$5.00

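### Section 1.22 tests raw weight within each arm in children aged 10-14 with no allowance for growth, which makes non-maintenance in the control arm easier to support

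*Combined protocol and SAP*

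**What the plan says.** Section 1.7 admits children by age: "Child age between 10-14". Cohort 2 uses the same criterion.

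Under the Cohort 1 primary analyses, section 1.22 states: "Two-way repeated measures ANOVAs will then be conducted to determine differences in BMI/percent over BMI, weight, and waist circumference, between the EFT and HT groups". The schedule follows: "Data points will be collected at weeks 2 (baseline), 7, 10, 14 (incentive program ends), 18, and 26 of the program". Four hypotheses are attached:

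- **Hypothesis 1:** both arms reduce from baseline while incentives run.
- **Hypothesis 2:** EFT reduces more than HT over the same period.
- **Hypothesis 3** (weeks 18 and 26): "The EFT group will maintain the reduction in BMI/percent over BMI, weight, and waist circumference from baseline".
- **Hypothesis 4** (weeks 18 and 26): "The HT group will not maintain the reduction in BMI/percent over BMI, weight, and waist circumference from baseline".

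Cohort 2 repeats the structure for sessions 19 and 20: "The HT group will not maintain the reduction in BMI/percent over BMI and weight from baseline".

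The plan does treat body mass index differently by age. The Cohort 1 regression paragraph lists the outcomes as "BMI for adults/percent over BMI for children, weight, waist circumference, and DD". Weight has no such split. The child's incentive in section 1.13 is also set in raw pounds: "Child receives this amount if he/she loses 1/2 lb that week". Growth is not mentioned anywhere as an influence on child weight.

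**The concern.** Children of 10-14 are growing, so their weight is expected to rise over several months even if their weight status does not change. Randomisation should make that rise equal in the two arms, and it then drops out of a comparison between arms. It does not drop out of a change from baseline within one arm, which is the form of hypotheses 1, 3 and 4.

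The direction is known in advance. Growth makes a reduction harder to show (hypothesis 1), makes maintenance in EFT harder to show (hypothesis 3) and makes non-maintenance in HT easier to show (hypothesis 4). A group of children with stable percent over BMI could appear to regain.

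This matters because maintenance after incentives end is the study's main question (section 1.5), and section 1.22 expresses it only through the two within-arm statements, hypotheses 3 and 4.

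**Working it through.** **1. Which hypotheses are exposed.** Write the mean change in child weight in an arm as T + G, where T is the change due to behaviour and G is growth.

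- Hypotheses 1, 3 and 4 concern T + G within an arm, so G stays in.
- Hypothesis 2, the group-by-time comparison and hypothesis 2 of section 1.4 concern (T_EFT + G) - (T_HT + G) = T_EFT - T_HT, so G cancels in expectation.

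**2. Schedule and goals (sections 1.3, 1.13 and 1.22).** The plan has no power calculation, SD or alpha to reproduce. Its incentive total can be reproduced, and this confirms 12 weekly goals in Cohort 1: 2 x (0.50 + 1.00 + 2.50 + 9 x 5.00) + 12 x 4.20 = 98.00 + 50.40 = $148.40, as stated in section 1.13.

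- Cohort 1: 12 goals x 0.5 lb = 6 lb. Weeks after incentives end: 26 - 14 = 12.
- Cohort 2: 8 goals (sessions 4-11) x 0.5 lb = 4 lb. Weeks after incentives end: 8 of phone sessions + 8 with no intervention = 16.

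**3. Which growth counts against a goal-level loss.** The goal is read off the scale. A child who meets every goal is therefore 6 lb (or 4 lb) lighter after any growth in the incentive weeks. Only later growth can erode that loss.

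**4. Size.** Assumption, not in the documents: growth of 2-5 kg/year. Growth in lb = rate x weeks / 52 x 2.2046.

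| | 2 kg/year | 5 kg/year | Goal-level loss | Share eroded |
|---|---|---|---|---|
| Cohort 1, 12 weeks | 2 x 12/52 x 2.2046 = 1.0 lb | 5 x 12/52 x 2.2046 = 2.5 lb | 6 lb | 17-42% |
| Cohort 2, 16 weeks | 2 x 16/52 x 2.2046 = 1.4 lb | 5 x 16/52 x 2.2046 = 3.4 lb | 4 lb | 34-85% |

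A child group that met every goal and then only grew would still be below baseline at the last visit, by 3.5-5.0 lb in Cohort 1 and 0.6-2.6 lb in Cohort 2.

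**5. Illustration of a within-arm test.** The plan specifies no test for hypothesis 4. Suppose non-maintenance were judged by a one-sample t test of weight change since incentives ended, two-sided at 0.05, with an SD of change of 2 kg (all assumed). With growth only and no true relapse, the noncentral t gives these chances of a significant regain:

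- Cohort 1 (20 per arm): 17% at 2 kg/year and 50% at 4 kg/year.
- Cohort 2 (10 per arm): 14% at 2 kg/year and 41% at 4 kg/year.

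For SDs of 1.5-3 kg at these two rates, the range is 10-74% in Cohort 1 and 9-64% in Cohort 2. Under the same growth, with an SD of 2 kg, a two-sample test of EFT against HT rejects in 5.1-5.3% of 20,000 simulated trials.

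**The case against.** The strongest reply is that the study is comparative. The planned ANOVAs look for differences between arms, section 1.4 predicts better maintenance in EFT than in control, and section 1.5 gives the purpose in the same terms. Growth does not bias any of these. Percent over BMI sits in the same hypotheses, so a divergence between it and weight would be visible. Raw weight is also what the child incentive rewards. All of this stands, and it limits the point to the within-arm hypotheses on child weight.

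It is also fair that no within-arm test or margin is stated. The rejection rates in step 5 of the working therefore illustrate one possible reading and are not properties of the plan. They concern regain since incentives ended, whereas the hypotheses speak of a reduction from baseline, part of which would remain.

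Four stronger readings are tempting but not supported:

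- **All 24 weeks of Cohort 1 growth count against the 6 lb.** This would give 34-85%, but it counts growth in the incentive weeks twice, since the raw-pound goal is already net of it.
- **Individual children would be labelled as failing to maintain.** The plan classifies no child; its analyses are of groups.
- **Growth tilts the trial towards EFT.** It acts on both arms and makes hypothesis 3 harder as well as hypothesis 4 easier.
- **Weight is the designated primary outcome.** Section 1.22 lists several measures under primary analyses and singles out none. That weight includes children's weight is inferred from the lack of any restriction, though it is the natural reading.

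**Conclusion.** The concern holds for hypotheses 1, 3 and 4 as applied to children's raw weight in Cohorts 1 and 2. Its existence and direction follow from the ages and the within-arm wording. Its size rests on the assumed 2-5 kg/year: 17-42% of a full goal-level loss in Cohort 1 and 34-85% in Cohort 2. The between-arm comparison and the parents' results are untouched, so this should be corrected but does not invalidate the design. The same growth caution applies to children's waist circumference in Cohort 1, for which no figure can be given from the documents.

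**What to change.** In section 1.22, for both cohorts:

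1. Test the child hypotheses on percent over BMI, and state the age- and sex-specific reference from which it is calculated. The documents do not define the measure, and its allowance for growth depends on that reference.
2. Report child raw weight descriptively, and keep raw weight in the primary analyses for parents only.
3. Base the maintenance conclusion on the EFT-versus-HT contrast in change after incentives end (Session 14 to 26 in Cohort 1, Session 11 to 20 in Cohort 2). Finding maintenance in one arm and not in the other is not a test of the difference between arms, and this is true of percent over BMI as well.
4. Add a note that within-arm changes in child waist circumference in Cohort 1 are open to the same growth effect.

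The cost is wording. Percent over BMI is already planned, and section 1.13 has height measured at Sessions 7, 10, 14, 18 and 26 in Cohort 1 and Sessions 3, 11, 19 and 20 in Cohort 2. The Cohort 1 Session 2 list names neither height nor weight, so the text should say whether baseline comes from Session 1 or Session 3, both of which measure them. The number of primary tests falls. The one small loss is that child raw weight, the measure the incentive rewards, is no longer formally tested. The incentive rules need no change for this purpose.
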